# RESEARCH PROPOSAL

## Research Title

**High Flow Nasal Cannula vs. Non-Invasive Ventilation in Post-Extubation Pediatric Cardiac Surgery Patients: A Randomized Controlled Trial**

### **Research Objectives:**

This study aims to compare the extubation success rate between the use of High Flow Nasal Cannula (HFNC) and Non-Invasive Ventilation (NIV) in pediatric patients post-cardiac surgery at the National General Hospital [name] (RSCM). Additionally, this study seeks to identify factors influencing extubation failure in high-risk patient populations, compare CICU length of stay, sedation usage and COMFORT scale between patients receiving HFNC and those receiving NIV.

### **Research Methodology:**

This study is a randomized controlled clinical trial involving two intervention groups: one receiving High Flow Nasal Cannula (HFNC) therapy using AirvoTM3 Nasal High Flow/HFNC System and the other receiving Non-Invasive Ventilation (NIV). The study population consists of pediatric patients admitted to the Cardiac Intensive Care Unit (CICU) at [name] National General Hospital (RSCM) following cardiac surgery. A total of 114 subjects will be enrolled, with 57 patients allocated to each group. Patients will be monitored for 24 hours post-extubation to evaluate the incidence of extubation failure and the associated risk factors. Reintubation will be performed in cases of respiratory failure or other complications requiring airway support.

### **Expected Outcomes:**

The use of HFNC is expected to achieve an extubation success rate that is comparable to NIV, while offering a lower risk of complications and enhanced patient comfort. The findings of this study are anticipated to provide significant evidence regarding the differences between these two modalities in preventing extubation failure.

### **Outcome of Study:**

The expected outcomes include a reduction in reintubation rates at 48 - 72 hours, 7 days, and 28 days post-extubation in the HFNC group compared to the NIV group. Additionally, this study aims to decrease mortality rates in the CICU and shorten the length of hospital stay for pediatric patients following cardiac surgery.

## CHAPTER 1 Introduction

### 1.1. Background

Congenital heart disease (CHD) is a significant global health concern, with a prevalence of 0.8–1.2% of total live births. In developed countries, post-cardiac surgery mortality rates among pediatric patients tend to be low. However, data from Indonesia, particularly from [name] National General Hospital (RSCM), indicate a significant mortality rate. Over the past 3–5 years, the post-cardiac surgery mortality rate among pediatric patients at RSCM has been approximately 13.6%, primarily due to complications such as low cardiac output syndrome (LCOS), arrhythmias, multi-organ dysfunction, and extubation failure. The incidence of extubation failure in pediatric cardiac surgery patients ranges from 9.7% to 17.6%, often associated with airway, neurological, cardiac, diaphragmatic, and electrolyte-related factors. Patients experiencing repeated extubation failure have a higher risk of mortality compared to those who either do not experience it or fail extubation only once. Therefore, identifying effective solutions to mitigate the risk of extubation failure is of critical importance.

Non-invasive ventilation (NIV) and high-flow nasal cannula (HFNC) are commonly implemented in healthcare centers to reduce the incidence of extubation failure. However, the effectiveness of HFNC in minimizing extubation failure among high-risk pediatric cardiac surgery patients remains uncertain, particularly in Indonesia. At RSCM, the systematic and widespread use of HFNC in managing post-cardiac surgery pediatric patients requires further investigation to establish its efficacy. This study aims to address this gap by comparing extubation success rates between HFNC and NIV at RSCM.

### 1.2. Relevance to Priority Research Topics

This research aligns with RSCM's priority health topics, specifically the improvement of intensive care and post-operative recovery in pediatric cardiac surgery patients. Investigating respiratory management strategies, such as HFNC versus NIV, directly contributes to enhancing healthcare quality at RSCM. If HFNC proves to be comparable to NIV in preventing extubation failure, its implementation could optimize patient recovery and reduce complication rates.

### 1.3. Research Problem Statement

Given the high incidence of extubation failure among pediatric post-cardiac surgery patients at RSCM, there is a pressing need to identify a more effective approach to prevent extubation failure. This study aims to answer the following research question: **Is HFNC as effective as NIV in preventing extubation failure in pediatric patients following cardiac surgery?**

---

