**Specific Objectives:**

1. To compare the extubation failure rate between patients receiving HFNC and those receiving NIV.
2. To identify factors influencing extubation success in each intervention group.

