#### **1.7. Strategic Research Outcomes**

##### **1.7.1. Internal Implementation at RSCM**

The results of this study are expected to be implemented at RSCM in the form of **Clinical Practice Guidelines (CPG)**, **Standard Operating Procedures (SOPs)**, or **Work Instructions (WIs)** for the management of pediatric post-cardiac surgery patients. The integration of HFNC as a routine care modality will be incorporated into RSCM's existing **clinical pathways**, supported by internal policies and regulations.

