	T-piece	Ventilator weaning method using a T-Piece without pressure support.	Categorical	Medical Records on the Method Used	
ABG 1 hour after NIV/HFNC	pH	Arterial blood pH measured 1 hour after initiation of NIV or HFNC.	Numeric	Arterial Blood Gas (ABG) Measurement	
	PCO2	Partial pressure of carbon dioxide (PaCO2) in blood, measured 1 hour after initiation of NIV or HFNC	Numeric	Arterial Blood Gas (ABG) Measurement	
	PaO2	Partial pressure of oxygen (PaO2) in blood, measured 1 hour after initiation of NIV or HFNC	Numeric	Arterial Blood Gas (ABG) Measurement	
	BE (Base Excess)	Base excess or deficit in blood, measured 1 hour after initiation of NIV or HFNC	Numeric	Arterial Blood Gas (ABG) Measurement	
	HCO3	Bicarbonate concentration in blood, measured 1 hour after initiation of NIV or HFNC	Numeric	Arterial Blood Gas (ABG) Measurement	
	PF ratio	Ratio of PaO2 to FiO2, measured 1 hour after initiation of NIV or HFNC	Numeric	Arterial Blood Gas (ABG) Measurement	
	OI/OSI	Oxygenation Index (OI) or Oxygen Saturation Index (OSI), measured 1 hour after initiation of NIV or HFNC	Numeric	Arterial Blood Gas (ABG) Measurement	
Successful Extubation	No Reintubation in 72 hours	Patient does not require reintubation within 72 hours after extubation	Categorical	Based on Clinical Observation	
Extubation Failure	Reintubation within 72 hours	Patient requires reintubation within 72 hours after extubation	Categorical	Based on Clinical Observation	
Reintubation	Reintubasi at 72 hours, 7 days and 28 Days	Frequency of patients requiring reintubation at 72 hours, 7 days and 28 days	Categorical	Based on Clinical Observation	
Mortality in CICU	Mortality During CICU Stay	Number of patient deaths during CICU hospitalization	Categorical	Based on Mortality Records	
Length of CICU Stay	Total Length of CICU Stay (in Days)	Total length of CICU stay measured in days	Numeric	Based on Hospital Records	
Length of Hospital Stay	Total Length of Hospital Stay (in Days)	Total length of hospital stay measured in days	Numeric	Based on Hospital Records	
Sedation usage	Duration of sedation (in Hours) and total dosage	Total duration of sedation after extubation measured in hours and total dosage	Numeric	Based on Hospital Records	
COMFORT scale	Patient's comfort during sedation post extubation	Patient's comfort measured in COMFORT behavioral scale	Categoric	COMFORT behavioural scale assessment	

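### The stated question is one of comparability, but the trial is sized to detect a 25-point difference and states no margin, so a non-significant result would leave the question open

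*Protocol*

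**What the plan says.** The protocol words its aim in three ways.

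- **Comparability.** Section 1.3 asks "Is HFNC as effective as NIV in preventing extubation failure in pediatric patients following cardiac surgery". Expected Outcomes states: "The use of HFNC is expected to achieve an extubation success rate that is comparable to NIV". Section 1.2 adds: "If HFNC proves to be comparable to NIV in preventing extubation failure, its implementation could optimize patient recovery".
- **Superiority of HFNC.** Outcome of Study expects "a reduction in reintubation rates at 48 - 72 hours, 7 days, and 28 days post-extubation in the HFNC group".
- **Neutral comparison.** The first specific objective in 1.5 is "To compare the extubation failure rate between patients receiving HFNC and those receiving NIV". The opening Research Objectives, the end of 1.1, the questions in 1.4 and the general objective in 1.5 are also neutral in direction.

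The sample size has one form only. Section 4.3 takes an HFNC failure rate of 0.17, adds 0.25 to reach 0.42 for the comparator (by implication NIV), and uses z-values of 1.96 and 0.84. It arrives at 51 per group, raised to 57 for 10% loss to follow-up. Section 4.5 repeats the 17% rate and the 25-point difference. The 0.25 is described as a difference to detect, not as a margin. Table 1 defines extubation failure: "Patient requires reintubation within 72 hours after extubation".

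On use of the results, section 1.7.1 says: "The integration of HFNC as a routine care modality will be incorporated into" the hospital's existing pathways.

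**The concern.** A question about being as effective is one of non-inferiority or equivalence. It is answered by showing that the plausible differences all lie inside a margin fixed beforehand. A test of difference asks whether zero can be ruled out. If it cannot, the result may reflect similar treatments or too few patients, and the test alone does not separate the two.

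This matters because the protocol expects HFNC to become routine care at the hospital and does not say which result would support that. A reader who starts from section 1.3 could take a non-significant result as the hoped-for finding, when a trial of this size would often give one even if HFNC were materially worse.

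The margin cannot simply be left to a later analysis plan, because it determines the sample size, and the sample size is fixed here on a different hypothesis.

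**Working it through.** **Inputs.** From section 4.3: failure rates 0.42 and 0.17, average 0.295, z-values 1.96 and 0.84, 51 per arm before the allowance for loss. From section 1.1: 9.7%, the low end of the published range for pediatric cardiac surgery. True failure rates in this trial are unknown, so a range is used. It includes the higher rates because section 4.4 enrols patients at high risk of failure.

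**1. The protocol's own figure.** n = [(1.96·√(2·0.295·0.705) + 0.84·√(0.42·0.58 + 0.17·0.83)) / 0.25]² = [(1.2641 + 0.5210) / 0.25]² = 50.98, so 51. Power for 42% versus 17% is 80.0% with 51 per arm and 84.3% with 57. The stated size therefore reproduces as a two-sided test of difference.

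**2. Precision if the arms are truly equal.** Standard error = √(2p(1−p)/51); 95% half-width = 1.96 × standard error. At p = 0.17: √(0.2822/51) = 0.0744, so the half-width is 14.6 points.

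**3. Smallest non-inferiority margin with 80% power** (one-sided 2.5%, equal true rates) = (1.96 + 0.8416) × standard error. At p = 0.17: 2.8016 × 0.0744 = 20.8 points.

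| True failure rate, both arms | 95% half-width, 51 per arm | Margin with 80% power, 51 per arm |
|---|---|---|
| 9.7% | 11.5 points | 16.4 points |
| 17% | 14.6 points | 20.8 points |
| 29.5% | 17.7 points | 25.3 points |
| 42% | 19.2 points | 27.4 points |

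**4. Equivalence needs more.** With 80% power and equal rates, the multiplier for a 90% interval is 1.645 + 1.2816 = 2.9266, and for a 95% interval 1.96 + 1.2816 = 3.2416. At 17% and 51 per arm these give about 21.8 and 24.1 points.

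**5. What a non-significant result could hide.** Assume 17% failure on NIV and 27% on HFNC, 51 per arm. Standard error under the null: √(2·0.22·0.78/51) = 0.0820. Under the alternative: √((0.1411 + 0.1971)/51) = 0.0814. Power = Φ((0.10 − 1.96·0.0820)/0.0814) = Φ(−0.746) = 0.228. The test would be non-significant about 77% of the time.

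**6. Direction of the hypothesis.** In the first calculation in 4.3 HFNC has the lower failure rate (0.17). In the second it has the higher reintubation rate (0.37, against a stated 0.15 for NIV, with 0.12 substituted). Table 1 defines failure as reintubation, so the two calculations point in opposite directions on what is essentially one outcome.

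**The case against.** The operative text is largely coherent. The research questions and objectives are neutral and match a two-sided test of difference. *Comparable* appears in an expectation and in a statement of relevance, not in an objective. Expected Outcomes also looks forward to evidence on how the two modalities differ, and 1.3 opens by seeking a more effective approach. On this view the fault is loose introductory wording. Much of that stands, and it is why rewording is enough. It does not remove the conflict, because 1.3 presents its sentence as the question the study aims to answer.

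Three stronger readings are tempting, and the documents do not support them.

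- *The trial cannot answer its question at all.* A significant difference would inform it, and a wide margin, if justified, would be supportable at this size.
- *The protocol plans to read a null result as comparability.* It nowhere says so.
- *The 80% power holds for 42% versus 17% and nothing else.* With 51 per arm, power is about 0.85 for 0.37 versus 0.12 and 0.87 for 0.10 versus 0.35, the rates substituted in the other two calculations in 4.3.

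The analysis plan is not shown and could contain a margin. It could not supply the patients that a tight margin needs.

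**Conclusion.** The point holds in this form: the question in 1.3 and the sample size in 4.3 and 4.5 rest on different hypotheses, and the powered test does not establish comparability. The size of the gap depends on assumed true rates. With 51 evaluable per arm, the 95% half-width runs from 11.5 to 19.2 points across failure rates of 9.7% to 42%. At 17%, the smallest non-inferiority margin with 80% power (20.8 points) exceeds the failure rate the protocol assumes for HFNC. The 77% chance of missing a 10-point deficit rests on an illustrative 17% versus 27%.

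This should be fixed. It is not graver than that, because the objectives already fit the design and no comparability claim from a null result is written into the protocol.

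**What to change.** State one primary hypothesis on 72-hour extubation failure as defined in Table 1, and bring Expected Outcomes, Outcome of Study and sections 1.2, 1.3, 4.3 and 4.5 into line with it.

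**Option A, preferred, because the sizing and sections 1.4 and 1.5 already support it.** Reword the question in 1.3 to: *Does the 72-hour extubation failure rate differ between HFNC and NIV in children after cardiac surgery?* Align the comparability wording and the expected reduction with this. Add: *The primary result is the risk difference (HFNC minus NIV) with its 95% confidence interval. A non-significant result is not evidence of comparability. The sample size gives 80% power for 42% versus 17% with 51 evaluable per arm; with one arm at 17%, a smaller excess in the other has less power.*

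**Option B, if comparability is kept.** State whether non-inferiority or equivalence is meant, justify and fix a margin before data are seen, and base the claim on the confidence limit. Report the supportable margins for 51 evaluable per arm (16.4, 20.8, 25.3 and 27.4 points for non-inferiority at 9.7%, 17%, 29.5% and 42%; wider for equivalence). The margin is the sponsor's to choose.

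Under either option, reconcile the direction of the HFNC and NIV rates across the calculations in 4.3.

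**Cost.** Option A changes wording only; sample size and objectives stay. Its downside is that a null result can no longer be called comparable. Option B is wording only if a margin that wide can be justified. A 10-point non-inferiority margin, as an illustration, would need n = 2.8016²·2p(1−p)/0.10², or 138, 222 or 327 evaluable per arm at 9.7%, 17% or 29.5%, before loss to follow-up.

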#### **1.4. Research Questions**

1. How does the extubation failure rate compare between HFNC and NIV in pediatric patients admitted to the CICU following cardiac surgery?
2. What factors influence extubation failure in pediatric patients receiving HFNC compared to those receiving NIV?

#### **1.5. Research Objectives**

**General Objective:** To determine the effectiveness of HFNC compared to NIV in preventing extubation failure among pediatric post-cardiac surgery patients at RSCM.

**Specific Objectives:**

1. To compare the extubation failure rate between patients receiving HFNC and those receiving NIV.
2. To identify factors influencing extubation success in each intervention group.

**Secondary Objectives:**

1. To compare CICU length of stay between patients receiving HFNC and those receiving NIV.
2. To compare sedation usage (duration and total dose) between patients receiving HFNC and those receiving NIV
3. To compare COMFORT scale between patients receiving HFNC and those receiving NIV

#### **1.6. Research Significance**

This study is expected to provide significant contributions to improving the quality of care for pediatric post-cardiac surgery patients at RSCM. The findings will generate valid data regarding the effectiveness of HFNC in preventing extubation failure, serving as a reference for selecting optimal respiratory therapy for these patients.

For RSCM, this research will facilitate the development of improved clinical care standards for pediatric post-cardiac surgery patients, reduce complication rates, and enhance recovery outcomes.

#### **1.7. Strategic Research Outcomes**

##### **1.7.1. Internal Implementation at RSCM**

The results of this study are expected to be implemented at RSCM in the form of **Clinical Practice Guidelines (CPG)**, **Standard Operating Procedures (SOPs)**, or **Work Instructions (WIs)** for the management of pediatric post-cardiac surgery patients. The integration of HFNC as a routine care modality will be incorporated into RSCM's existing **clinical pathways**, supported by internal policies and regulations.

### **1.7.2. External Adaptability outside RSCM**

The findings of this study have the potential to be adopted by other institutions outside RSCM, particularly hospitals that manage pediatric cardiac surgery cases. By demonstrating the effectiveness of HFNC, other hospitals may implement similar modalities to enhance the quality of care for pediatric post-cardiac surgery patients

## CHAPTER II Literature Review

Pediatric patients undergoing cardiac surgery are at high risk of developing respiratory complications, particularly following extubation. Unsuccessful extubation can lead to respiratory failure, increasing the need for reintubation and further medical interventions. Extubation failure is defined as the necessity for reintubation within 72 hours after planned extubation. Several studies have reported that the incidence of extubation failure in pediatric post-cardiac surgery patients ranges from 9.7% to 17.6%, depending on factors such as cardiopulmonary bypass (CPB) duration, congenital heart disease severity, and high inotropic support requirements. One potential strategy to reduce this rate is the implementation of non-invasive ventilation (NIV) or high-flow nasal cannula (HFNC) as a transitional modality before initiating low-flow oxygen therapy. However, the effectiveness of these approaches remains controversial, particularly in high-risk post-cardiac surgery populations. Furthermore, at the RSCM Cardiac ICU, a modified form of NIV is still in use, which may not be ideal due to the potential for inadequate airflow delivery.

### ***High Flow Nasal Cannula (HFNC)***

HFNC is one of the methods used to support post-extubation patients to reduce the need for invasive intubation. HFNC delivers high-flow oxygen via a nasal cannula, equipped with optimal humidification and heating, thereby increasing patient comfort and reducing respiratory workload. HFNC also helps improve oxygenation and reduce the need for invasive mechanical ventilation. Research conducted by Mayfield et al. showed that the use of HFNC in pediatric patients with bronchiolitis can significantly reduce the need for admission to the pediatric intensive care unit (PICU) by up to fourfold compared with the use of low-flow oxygen therapy. HFNC has also been recognized as a safe modality for use in non-ICU settings, including in pediatric wards. McKiernan et al. emphasized that HFNC can reduce the rate of re-intubation in pediatric patients with bronchiolitis, as well as improve oxygen saturation without the risk of side effects such as pneumothorax or bradycardia.

### ***Non-Invasive Ventilation (NIV)***

NIV is a respiratory support technique that utilizes positive pressure ventilation without invasive intubation. It is commonly employed in patients with acute respiratory distress to maintain airway patency and enhance gas exchange. Although NIV has been proven effective in preventing extubation failure in pediatric patients, it has several limitations. The use of masks or nasal interfaces in NIV can cause discomfort, particularly in infants and younger children, and may also increase the risk of air leakage, reducing the efficacy of the therapy. A study by Thille et al. found that factors such as prolonged cardiopulmonary

bypass duration and high inotropic support postoperatively increased the risk of extubation failure in patients receiving NIV. Additionally, research by Miura et al. indicated that neonates experiencing extubation failure due to cardiovascular complications were at a higher risk of repeated extubation failure, which further elevated mortality risk.

[figure not shown]
### **Comparison of the Effectiveness of HFNC and NIV**

Studies comparing HFNC and NIV in pediatric post-cardiac surgery patients have yielded mixed results. Some research supports HFNC as a more comfortable and easier-to-implement modality, particularly due to its less invasive nasal cannula interface compared to the masks used in NIV. Furthermore, HFNC is considered more user-friendly in non-ICU settings. Conversely, NIV has been utilized for a longer duration in intensive care settings and is known for providing stable positive pressure, which helps prevent alveolar collapse and improves gas exchange in patients with compromised pulmonary function.

[figure not shown]
A study by Zhou et al. (2024) found that HFNC significantly reduced reintubation risk (RR = 0.36,  $P < 0.00001$ ) and shortened ICU stay duration (MD = -4.75,  $P = 0.04$ ). Similarly, research by Elmitwalli et al. (2024) reported that HFNC decreased reintubation rates (RR = 0.45,  $P < 0.01$ ), mortality (RR = 0.31,  $P < 0.01$ ), as well as length of hospital stay (-8.76 days,  $P < 0.01$ ) and ICU stay (-4.63 days,  $P = 0.04$ ). However, compared to conventional oxygen therapy, no significant differences were observed in reintubation rates. A study by Kuitunen (2023) concluded that there was insufficient evidence to establish a definitive difference in reintubation rates and other clinical outcomes between different non-invasive ventilation strategies, due to high bias risk and limited study numbers.

The debate continues regarding which modality is more effective in reducing extubation failure and mortality. HFNC provides benefits for patients with moderate-to-severe respiratory failure risk, whereas NIV may be more suitable for patients with severe pulmonary conditions. Further research is required to determine the optimal post-extubation strategy for pediatric post-cardiac surgery patients.

